## **Evaluation**

### **Data analysis**

The *R* software will be used for data analyses. Descriptive statistics will be used to analyze the demographic data, baseline information, and adherence with orthosis wearing. The linear mixed-effects model regression will be used as the omnibus test for examination of effect of intervention involving orthosis across time in comparison of that without. The

Orthosis for stroke  
Protocol Number: 1309M42881

systematic or fixed effects of this study are group assignment and time. Main effect of the two factors and the interaction effect between the two will be explored. Study participants will be considered and added into the model as the random effects.

General linear regression model will be used to determine effects of experimental conditions between the two groups. Data obtained from the pretest will first be used to examine if there are differences in outcome measures between the two groups. It will also serve as a covariate while examining difference between the two groups at the posttest 1. Data from the posttest 1 will serve as a covariate while examining difference between the two groups at the posttest 2. The *paired t* test will be used to examine difference within each group for each intervention period across time.

Interim monitoring of the data will occur after 16 participants complete the study. If the study results indicate a significant decline in functional performance for either group across the 12-week study, the study will be terminated. If there are serious adverse effects, the study would be terminated.

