**Data collection plan and schedule.** The timing of screening, randomization, and follow-up visits are illustrated in Figure 2. The primary investigator will screen potential participants' eligibility using the Mini-Mental Status Examination (MMSE), the Short Form Fugl-Meyer (S-FM), and ROM. There will be three time points for data collection (pretest, posttest 1, and posttest 2). Trained occupational therapy students recruited from the University of Minnesota and University of Puget Sound will serve as the blinded evaluators to implement all assessments except the COPM for each research site. The primary investigator will administer the COPM to obtain information that will be used to guide future interventions.

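### The omnibus mixed model names no deciding term, and no planned analysis gives a total orthosis effect at posttest 2 that is regression-adjusted for pretest

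*Combined protocol and SAP*

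**What the plan says.** In the Data analysis section, "The linear mixed-effects model regression will be used as the omnibus test for examination of effect of intervention involving orthosis across time". The fixed effects are group assignment and time. On how these are used, the plan says that "Main effect of the two factors and the interaction effect between the two will be explored". On the random part, "Study participants will be considered and added into the model as the random effects". The section does not say which term or contrast answers the orthosis question, how the factors are coded, or whether the groups share a pretest mean.

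The Study plan section fixes the visits: "There will be three time points for data collection (pretest, posttest 1, and posttest 2"). Table 1 labels them O1, O2 and O3 and puts O1 before any treatment.

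Separate between-group linear regressions are also planned. Of the pretest the plan says "It will also serve as a covariate while examining difference between the two groups at the posttest 1". For the final visit, "Data from the posttest 1 will serve as a covariate while examining difference between the two groups at the posttest 2".

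Hypothesis 1 in the Objectives section is about greater improvement in orthosis wearers, that is, a difference in change. The sample size section calls the study a pilot whose results will supply effect sizes for a later study.

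**The concern.** The same wording allows several different numbers to be reported as the orthosis effect. One listed candidate, the group main effect, includes a visit at which no treatment effect can exist. Another, the interaction, asks the right question but is equivalent to comparing unadjusted change from pretest, which is less precise than adjusting for pretest.

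The separate regressions close this gap at posttest 1 but not at posttest 2. The final visit is where the orthosis plus task-oriented therapy is compared with the therapy alone, which is the study's stated primary purpose.

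The choice also reaches the next trial. If a main effect of two thirds the true size were carried forward at the same SD, the required sample size would grow by (3/2)² = 2.25.

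**Working it through.** **The plan's own figure.** Enrolment of 30 matches the allocation scheme, 3 severity groups × (5 + 5) = 30, or 15 per arm. The plan states no alpha, power, effect size, SD or correlation, so there is no power calculation to reproduce.

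**Inputs.** From the documents: 15 per arm, three visits, participant as random effect. Assumed for illustration: a random intercept (one common between-visit correlation r), SD 1, a true effect of 0.8 SD at both posttests, no expected pretest difference, two-sided 0.05. Power uses the noncentral t with 28 df. Let D1, D2 and D3 be the observed A-minus-B differences at O1, O2 and O3, and d2 and d3 the true effects at the posttests. Each observed difference has variance 2/15, and any two have correlation r.

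**1. Group main effect.** Averaged over visits it estimates (0 + d2 + d3)/3 = 2/3 × (d2 + d3)/2. With 0.8 at both posttests this is 1.6/3 = 0.53 SD. Its variance is (2/15)(1 + 2r)/3, which gives power of 41% at r = 0.5 and 35% at r = 0.7. Under treatment coding with pretest as reference, the group coefficient is D1 alone. In a simulation with a true effect of 0.8, the averaged term came out at 0.54, the treatment-coded group coefficient at 0.02, and the group-by-posttest 1 interaction at 0.77.

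**2. Mean of the two posttests, free or adjusted pretest (1 df each).**
- Free: (D2 + D3)/2 − D1, variance (2/15)[(1 + r)/2 + 1 − 2r].
- Adjusted: (D2 + D3)/2 − r·D1, variance (2/15)[(1 + r)/2 − r²].

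At r = 0.5 the brackets are 0.75 and 0.50, so the variances are 0.100 and 0.067. At r = 0.7 they are 0.45 and 0.36, so the variances are 0.060 and 0.048. The adjusted-to-free ratios are 0.67 and 0.80.

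**3. O3 alone.**
- Free: D3 − D1, variance (2/15) × 2(1 − r) = 0.133 at r = 0.5 and 0.080 at r = 0.7.
- Adjusted: D3 − r·D1, variance (2/15)(1 − r²) = 0.100 and 0.068.

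| Contrast, true effect 0.8 SD | r = 0.5 | r = 0.7 |
|---|---|---|
| Mean of O2 and O3, free pretest | 69% | 88% |
| Mean of O2 and O3, adjusted | 85% | 94% |
| O3 alone, free pretest | 56% | 78% |
| O3 alone, adjusted | 69% | 84% |

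**4. What the posttest 2 regression estimates.** With posttest 1 as covariate, the group coefficient targets d3 − r·d2, because the within-group slope of O3 on O2 is r. With 0.8 at both visits this is 0.8(1 − 0.5) = 0.40 at r = 0.5 and 0.8(1 − 0.7) = 0.24 at r = 0.7. It describes the second phase given the posttest 1 value, not the total difference of 0.8 since assignment.

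**The case against.** The strongest reply is that the plan never says it reads the orthosis effect from the group main effect. The sentence also lists the interaction, which is undiluted and is what hypothesis 1 calls for. That stands. A reader might infer that the planned test dilutes the effect by a third. The documents do not support this, because no term is named as deciding. The one-third loss also holds only for the averaged main effect, and only against the mean of the two posttest effects.

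A reader might also infer that the plan wastes the pretest throughout. It does not: the posttest 1 regression has variance (2/15)(1 − r²), which is the full adjusted precision at O2. The loss lies in the mixed model and at O3.

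Setting the 2-df interaction test (59% at r = 0.5, 82% at r = 0.7) against the adjusted 1-df average (85%, 94%) would overstate the gain, since part of that gap is degrees of freedom. Like for like, adjustment adds about 16 and 6 percentage points.

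Finally, equal pretest means cannot be treated as guaranteed. The Treatment allocation section assigns groups at the screening session, and Table 1 shows random assignment ahead of O1. The investigator who assigns also administers the COPM, a self-report measure of the primary endpoint. If assignment is known by then, forcing a common pretest mean could introduce bias. This stands and qualifies the fix.

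The pilot purpose softens the matter but does not remove it, because the pilot is meant to yield effect sizes.

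**Conclusion.** The point holds as a fault of specification and precision, not as a wrong test. The omnibus analysis needs a named contrast. The group main effect should not be that contrast; this needs no assumption beyond no expected group difference at pretest.

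The plan offers two between-group results at O3: a change-type contrast with pretest means left free, and a regression on posttest 1 that targets something else. Neither is a pretest-adjusted total effect.

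The precision gain is moderate and shrinks as visits become more correlated: for O3 alone, 56% to 69% at r = 0.5 and 78% to 84% at r = 0.7. Effect size, SD, correlation and alpha behind these figures are assumed. Changing the analysis is worthwhile because it costs almost nothing.

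**What to change.** State the omnibus analysis as one repeated-measures mixed model with visit as a category and adjustment for pretest. Either of two forms will do: O2 and O3 as outcomes with pretest as a covariate and a separate pretest slope at each visit, or all three visits as outcomes with one common O1 mean and group terms only at O2 and O3.

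Report the A-minus-B differences at O2 and O3 with 95% intervals as the orthosis effects, plus their average if a single figure is wanted. Say that the group main effect will not be interpreted. If the posttest 2 regression on posttest 1 is kept, label it as a second-phase comparison.

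Obtain pretest values, at least the COPM, before the assignment is revealed. If that cannot be done, state the equal-pretest assumption as a limitation for that measure.

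The analysis change takes a few sentences and some lines of R, with no extra participants, visits or data. The only procedural cost is the order of pretest and disclosure of assignment.

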## Methodology

### Study design

This study will employ a randomized, single-blinded, two-group, repeated measure design (Table 1).

Table 1. *Experimental design of the internal pilot study*

Group/Week			Week 1	Week 2-7	Week 8	Week 9-14	Week 15
M	R	A	O1	Orthosis	O2	Orthosis+OTTO	O3
M	R	B	O1	No treatment	O2	OTTO	O3

*Note.* M = matching with severity of motor function of the upper extremity; R = random assignment; O1,2,3 = time points for outcomes measures; Orthosis = six weeks of forearm rotation-assist orthotic intervention; OTTO = six weeks of OT task-oriented approach intervention.

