### Objectives

The primary purpose of this study is to investigate the efficacy of a forearm rotation orthosis combined with the OT task-oriented approach for persons with a hemiparetic arm. Hypotheses of this study are that 1) participants who wear the forearm rotation orthosis will demonstrate significantly greater improvement in functional performance and active range of motion of forearm rotators compared to those who do not; 2) all participants who receive the OT task-oriented approach intervention will demonstrate significant improvement in functional performance; and 3) all participants who receive the OT task-oriented approach intervention will demonstrate significant improvement in motor function of the upper extremity.

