### **Sample size estimation**

We plan to enroll 30 participants in the study. Based on anticipated number of screen failures and/or withdrawals, the maximum number of participants whom we will consent in order to achieve the scientific objectives of this study is 40. Note that the number of participants described above is a rough estimate of the sample size needed, since there is no evidence to address the primary question of interest. This proposed project involves pilot/preliminary investigation, which will be used to calculate the effect sizes that need to be used for the future study.

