## Study plan

**Intervention.** Participants in the Group A will experience the orthotic intervention followed by the orthosis plus OT task-oriented approach intervention. Participants in the Group B will first undergo a period of no treatment followed by the OT task-oriented approach only (Figure 3).

[figure not shown]

Figure 3. Flowchart for the proposed protocol.

**Use of the Nike + FuelBand as monitor and placebo.** The Nike+ FuelBand will serve as a monitor for all participants throughout their study period. The FuelBand is a commercially available wristband designed to measure activities throughout a day. The

Orthosis for stroke  
Protocol Number: 1309M42881

wristband is available in three sizes. Researcher will adjust the length for each participant, by removing 8mm link or adding up to 16mm to each wristband.

All participants will wear the Nike+ FuelBand at the wrist level throughout the study period and will be informed that the wristband is used to monitor their use of the arms during a day. Participants experiencing the orthotic intervention (Group A) will wear the forearm rotation orthosis on top of this wristband. All participants will receive weekly phone calls from the investigator reminding them to recharge the wristband because the wristband needs to be recharged by connecting to a computer or any device with USB port every 4-7 days.

Conditions involving OT task-oriented approach intervention consists of 18 hours of intervention time (three one-hour or two 1.5-hour session per week) of functional and motor training. Each session will concentrate on how to engage the affected arm actively, effectively, and efficiently in functional tasks that are meaningful to the participant. Suggested evaluation and intervention procedures for the OT task-oriented approach are illustrated in Figure 4 and 5.

[figure not shown]

Figure 4. Flowchart for suggested evaluation procedure for OT task-oriented approach.

Copied from Almhawi (2011) with permission.

[figure not shown]

Figure 5. Flowchart for suggest treatment for OT task-oriented approach. Copied from Almhawi (2011) with permission.

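### The posttest 2 comparison adjusts for posttest 1, which follows six weeks of orthosis wear in Group A only, so its group coefficient is biased for both the total effect and the phase 2 increment

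*Combined protocol and SAP*

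**What the plan says.** The Data analysis section gives between-group effects to a general linear regression at each posttest. At the first, the covariate is the pretest: "It will also serve as a covariate while examining difference between the two groups at the posttest 1". At the second it is not: "Data from the posttest 1 will serve as a covariate while examining difference between the two groups at the posttest 2".

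What happens between those visits is set out in Study design, Table 1 ("Orthosis = six weeks of forearm rotation-assist orthotic intervention") and in Study plan. For one arm: "Participants in the Group A will experience the orthotic intervention followed by the orthosis plus OT task-oriented approach intervention". For the other: "Participants in the Group B will first undergo a period of no treatment followed by the OT task-oriented approach only".

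The same section plans a linear mixed model with group, time and a participant random effect as the omnibus test, of which it says: "Main effect of the two factors and the interaction effect between the two will be explored". It names no contrast at posttest 2.

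The Objectives section states: "The primary purpose of this study is to investigate the efficacy of a forearm rotation orthosis combined with the OT task-oriented approach". Under Sample size estimation the study is called pilot work, "which will be used to calculate the effect sizes that need to be used for the future study".

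**The concern.** Posttest 1 is measured after randomisation, once one arm has had the device and the other nothing. Hypothesis 1 in the Objectives predicts that the device changes outcomes, so by the plan's own premise this covariate is affected by assignment. Adjusting for it removes part of the treatment effect from the posttest 2 comparison.

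Posttest 2 is the only visit that compares orthosis plus task-oriented therapy with the therapy alone. If the orthosis works in phase 1 and scores correlate positively over time, the regression understates its total effect there. The sign reverses if d2 < b·d1. The plan does not say whether it wants the total effect or the phase 2 increment, and the coefficient delivers neither. An effect size taken from it would carry the error into the next study's sample size.

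**Working it through.** **Inputs.** From the documents: the visit timing (Study design, Table 1), planned enrolment of 30 (Sample size estimation), and three severity classes with 5 per arm (Treatment allocation), so 3 × 5 = 15 per group. The documents give no effect size, SD, correlation or alpha. The 30 is described as a rough estimate, so there is no power calculation to reproduce. Assumed here: SD 1 at each visit, equal correlation r between visits (so b = r), two-sided 5%, and r from 0.3 to 0.9.

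**Formula.** An adjusted group difference is the raw difference in the outcome minus the slope times the raw difference in the covariate:

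- planned coefficient = d2 − b·d1
- bias for the total effect d2 = −b·d1
- bias for the phase 2 increment d2 − d1 = (1 − b)·d1

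If d1 = 0 there is no bias for either target. If b = 0 the total is unbiased, and if b = 1 the increment is unbiased.

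**Benefit of 0.8 SD at posttest 1, fully kept (d1 = d2 = 0.8).** The planned estimate is 0.8 − 0.8r. Percentages come from 20,000 simulated trials per scenario.

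| r | 0.3 | 0.5 | 0.7 | 0.8 | 0.9 |
|---|---|---|---|---|---|
| Planned estimate (SD) | 0.56 | 0.40 | 0.24 | 0.16 | 0.08 |
| Planned, significant benefit | 29% | 19% | 13% | 9% | 6% |
| Pretest-adjusted estimate (SD) | 0.80 | 0.80 | 0.80 | 0.80 | 0.80 |
| Pretest-adjusted, significant benefit | 59% | 67% | 83% | 93% | >99% |
| Group-by-time test (2 df), significant | 45% | 59% | 82% | 95% | >99% |

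The true increment here is zero. So the first row is also the bias for the increment, and the second is the rate of falsely declaring a phase 2 benefit.

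**Other paths.**

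| r | 0.3 | 0.5 | 0.7 | 0.8 | 0.9 |
|---|---|---|---|---|---|
| Growing, d1 = 0.4, d2 = 0.8: 0.8 − 0.4r | 0.68 | 0.60 | 0.52 | 0.48 | 0.44 |
| Falling, d1 = 0.8, d2 = 0.4: 0.4 − 0.8r | 0.16 | 0.00 | −0.16 | −0.24 | −0.32 |
| Falling: significant harm, planned | 1% | 2–3% | 8% | 16% | 43% |

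In the growing case the total is 0.8 and the increment 0.4; no estimate equals either. In the falling case the total is +0.4, and pretest adjustment shows significant harm in about 0% of trials.

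**Smaller effect (d1 = d2 = 0.5; 6,000 simulated trials).** At r = 0.7 the planned coefficient averages 0.149 and is significant in 7.9% of trials. Pretest adjustment gives 0.505 and 44.9%. The planned model rejects the true zero increment in 12.1%, 7.9% and 5.9% of trials at r = 0.5, 0.7 and 0.9. At 1,000 per group (500 trials) the coefficient is still 0.149, so the bias does not shrink with sample size. Keeping posttest 1 and adding the pretest does not repair it: 0.297, against a total of 0.50 and an increment of 0. With d1 = 0 and d2 = 0.5 the planned model gives 0.501, that is, no bias.

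**Can the 2-df interaction test stand in?** Its power depends on the squared deviations of the three visit differences from their mean.

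- Kept (0, 0.8, 0.8), mean 0.533: 0.284 + 0.071 + 0.071 = 0.427.
- Wholly lost (0, 0.8, 0), mean 0.267: 0.071 + 0.284 + 0.071 = 0.427.

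The power is the same in both, so the test cannot tell a lasting benefit from a vanished one.

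**Future study.** Per group, n = 2 × (1.96 + 0.84)² × (1 − r²)/d². If a kept benefit d is carried forward as (1 − r)·d, n is multiplied by 1/(1 − r)². For d = 0.5, 80% power and a pretest-adjusted analysis:

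| r | Correct n | n from the planned estimate | Ratio |
|---|---|---|---|
| 0.3 | 58 | 117 | 2.0 |
| 0.5 | 48 | 189 | 4.0 |
| 0.7 | 32 | 356 | 11 |

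**The case against.** **The regression was meant for phase 2.** Each posttest is adjusted for the test before it, and paired tests are run period by period, so this is a plausible reading. On it, the falling case has a true increment of −0.4, and the negative estimates at r = 0.7 to 0.9 have the right sign. That stands: the harm percentages are errors only for the total effect. But the increment is still misestimated by (1 − b)·d1. In the falling case at r = 0.3 the estimate is +0.16 against a true −0.4. The increment bias does become small at high r (0.08 SD at r = 0.9 with d1 = 0.8).

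**d1 may be small.** The orthosis is removed at evaluations, so performance tests capture only carry-over. At d1 = 0.2 the total-effect bias is −0.06 to −0.18 SD, and even pretest adjustment has only about 8–21% power. This is fair as to size. However, the Motor Activity Log concerns real-world use of the arm, which taking the orthosis off for the visit does not undo.

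**The mixed model covers it.** With time as a factor, it contains the group difference in change from pretest to posttest 2, significant in about 45%, 57%, 79%, 93% and over 99% of trials in the kept case. This is real mitigation. But time coding is not stated, the contrast is not named, and the plan gives the between-group determination to the regression.

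**It is a pilot with no analysis designated primary.** True, and the plan does not say which model will supply the effect size, so the inflation factors are conditional on that choice. A pilot meant to estimate effects is nevertheless harmed more by bias than by low power.

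**Conclusion.** The concern holds. As written, the posttest 2 regression estimates d2 − b·d1, which is neither the total effect nor the phase 2 increment whenever the orthosis has had any effect by posttest 1 and b lies strictly between 0 and 1. The first condition is what hypothesis 1 predicts; the second is usual for repeated scores measured with error.

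The share of the posttest 1 difference removed is b, which the documents do not allow one to fix. Over r = 0.3 to 0.9, under the equal-SD, equal-correlation assumption, 30% to 90% of a fully kept benefit disappears from the estimate.

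The defect is confined to this one regression. The pretest-adjusted posttest 1 comparison and the mixed model do not condition on posttest 1. It should still be corrected before analysis: this is the only between-group comparison explicitly specified at the visit that serves the primary purpose.

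**What to change.** Replace the posttest 2 covariate sentence with: *The pretest value is the covariate for the between-group comparison at both posttest 1 and posttest 2.*

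Name two mixed-model contrasts in advance, with time as a three-level factor:

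1. the group difference in change from pretest to posttest 2 (total effect);
2. the group difference in change from posttest 1 to posttest 2 (phase 2 increment).

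State that the effect size for the future study comes from the pretest-adjusted posttest 2 comparison. In the simulated d1 = d2 = 0.5, r = 0.7 case, that comparison recovered the total (0.505). The posttest 1 to posttest 2 change, regressed on group and pretest, recovered the zero increment (−0.004, with 5.2% rejection).

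The cost is analysis wording only. The pretest is already scheduled for every participant, so no data, visits or participants are added.

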### **Treatment allocation**

Participants who are eligible and willing to participate in this study will first be matched with the severity of the motor function of the involved upper extremity measured by the upper extremity subscale of the Short Form Fugl-Meyer Motor Function Assessment. Participants will be classified as mild, moderate, and severe groups. Participants in each group will then be randomized in a 1:1 allocation ratio to either the Group A or B (Figure 1). The primary investigator, [name], will randomly assign eligible participants at the screening session using sealed envelopes with an equal number of both intervention

conditions to balance group size (10 for each matched group with 5 Group As and 5 Group Bs).

[figure not shown]

Figure 1. Study schematic for treatment allocation.

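### The interim rule looks at functional decline over the whole 12 weeks, so a decline during the orthosis-only period can be largely masked by later gains from the therapy

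*Combined protocol and SAP*

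**What the plan says.** The Data analysis section provides for one look: "Interim monitoring of the data will occur after 16 participants complete the study". The rule is: "If the study results indicate a significant decline in functional performance for either group across the 12-week study, the study will be terminated". A separate sentence ends the study for serious adverse effects. The rule does not name the test, the alpha, the outcome measure or the time contrast.

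The Study design table has two six-week periods with assessments before, between and after them (O1, O2, O3). The first gives Group A "six weeks of forearm rotation-assist orthotic intervention"; the second gives both groups "six weeks of OT task-oriented approach intervention". The Study plan confirms the sequences: "Participants in the Group A will experience the orthotic intervention followed by the orthosis plus OT task-oriented approach intervention", and "Participants in the Group B will first undergo a period of no treatment followed by the OT task-oriented approach only". The therapy amounts to 18 hours.

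The second hypothesis under Objectives is that "all participants who receive the OT task-oriented approach intervention will demonstrate significant improvement in functional performance".

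The Data analysis section also plans a between-group regression at posttest 1 adjusted for the pretest, one at posttest 2 adjusted for posttest 1, and paired t tests within each group, period by period. None of these is linked to the interim rule.

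**The concern.** Only O1 to O2 shows what the orthosis does without the therapy. The interim rule spans both periods. If the orthosis lowers function in the first period and the therapy raises it in the second, the rule sees only the net result. The better the therapy works, the less likely the rule is to register the earlier loss.

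The protocol foresees functional harm: its section on potential risks of the orthosis lists restricted arm movement during functional tasks. The interim look is the only planned examination of outcome data for functional decline while the trial is running. The O2 data that bear most directly on the question will already have been collected by then, but the rule as worded does not call on them.

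**Working it through.** **No figure to reproduce.** The plan gives no alpha, power, effect size or SD for the interim look. The only arithmetic check is the duration: 6 + 6 = 12 weeks, so the rule covers both periods.

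**Inputs from the documents.** The look comes at 16 completers, and participants are "randomized in a 1:1 allocation ratio to either the Group A or B". That gives about 16 / 2 = 8 per group if the split is even.

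**Assumptions (not in the documents).**
- Two-sided alpha 0.05, counting only the decline side (0.025).
- One outcome with the same SD at each visit.
- Correlation r between visits of 0.5 to 0.7.
- Loss of 0.8 SD by O2 in Group A, with no change in Group B over that period.
- Therapy gain from O2 to O3 of 0.2 to 1.0 SD.

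**Formulas.**
- Within Group A: paired t with 7 df, critical value 2.365. Standardised change dz = net change / sqrt(2(1 − r)); noncentrality = dz × sqrt(8). The divisor is 1.000 at r = 0.5 and 0.775 at r = 0.7.
- A versus B at O2, adjusted for pretest: residual SD = sqrt(1 − r²), which is 0.866 and 0.714; noncentrality = −0.8 / (residual SD × sqrt(2/8)), with 13 df and critical value 2.160.

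**Worked example, gain 1.0 SD, r = 0.5.** Net change = −0.8 + 1.0 = +0.2 SD; dz = 0.2; noncentrality = 0.2 × 2.828 = 0.57. The probability of a significant decline is 0.7%.

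**Probability of a significant decline, loss 0.8 SD by O2**

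| Contrast | Therapy gain | Net change | r = 0.5 | r = 0.7 |
|---|---|---|---|---|
| A, O1-O3 | 1.0 SD | +0.2 | 0.7% | 0.5% |
| A, O1-O3 | 0.8 SD | 0 | 2.5% | 2.5% |
| A, O1-O3 | 0.5 SD | −0.3 | 11.1% | 15.7% |
| A, O1-O3 | 0.2 SD | −0.6 | 31.2% | 47.2% |
| A, O1-O2 | none yet | −0.8 | 49.6% | 70.8% |
| A versus B at O2, adjusted | none yet | −0.8 | 40.2% | 54.5% |

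When the gain equals the loss, the O1-O3 test fires no more often than it would by chance (2.5%). With a gain of 0.5 SD it still fires less than a quarter as often as the O1-O2 test (11.1 / 49.6 = 0.22; 15.7 / 70.8 = 0.22). With a gain of 0.2 SD the shortfall is moderate.

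**False signals.** With no true change, one measure and the O1-O3 contrast in both groups, the chance of at least one significant decline is 1 − 0.975² = 4.9%. Adding O1-O2 in each group and A versus B at O2 makes five contrasts. Whatever their correlation, the chance is then at most 5 × 0.025 = 12.5%.

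**The case against.** **The rule may already work period by period.** No test is named, and the sentence just before the interim paragraph plans paired t tests for each period. Used at the interim look, those would include O1-O2 in Group A, and most of the masking would go. This reading is possible. But that sentence speaks of single periods and the interim rule speaks of the full 12 weeks, so O1-O3 is the more natural reading. If the per-period reading is meant, the text should say so.

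**The effect sizes are chosen.** True. The lowest probabilities describe participants who end 0.2 SD above where they started, and with a small therapy gain the O1-O3 test keeps much of its sensitivity. The amount of masking depends on the gain. Its direction follows from the design and hypothesis 2.

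**Other safeguards exist.** There is the stop for serious adverse effects, safety monitoring throughout by the academic advisor, regular phone calls, and the instruction to remove the orthosis and report symptoms. They reduce what is at stake, but none is a data-based look at functional decline. The orthosis is also off at evaluations, so performance tests at O2 would not directly show restriction while it is worn. That limits what the Wolf test can reveal at O2; the Motor Activity Log and the COPM concern everyday life.

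**A stronger reading to resist.** A reader might infer that a stop caused by Group B alone would be spurious because that group never wears the orthosis, and that the Group B trigger should go. The documents do not support this. They never limit the rule to harm from the orthosis. Group B spends six weeks untreated, under an eligibility criterion that bars other rehabilitation, so a decline there is a legitimate protection signal. If the therapy does add 1.0 SD, Group B's chance of a significant O1-O3 decline is below 0.001% per score, so the trigger is nearly inert. Recasting the whole rule as A versus B would miss a decline shared by both groups.

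**Conclusion.** The point holds in a limited form. On its most natural reading, the interim rule is poorly placed to detect a functional decline that occurs in the orthosis-only period, provided the therapy then works as hypothesis 2 expects. For a loss of 0.8 SD, detection in Group A falls from 50-71% at O2 to 11-16% over O1-O3 with a 0.5 SD gain, and to under 1% with a 1.0 SD gain. These figures rest on an assumed even split, alpha, correlation, common SD and effect sizes.

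It would go too far to say that the rule cannot see orthosis harm. It keeps some sensitivity when the therapy gain is small, and the unnamed test leaves a per-period reading open. This is an inexpensive improvement to the interim analysis, not a flaw that invalidates the trial.

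**What to change.** Keep the 12-week criterion for either group, including Group B. In the same paragraph of Data analysis:

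1. Add the O1-O2 change within each group to the interim analysis.
2. Add the pretest-adjusted A-versus-B comparison at posttest 1, which the section already plans for the final analysis, using everyone with O2 data at that point and not only the 16 completers.
3. Name the measure that stands for functional performance, the test and the significance level, and say that the existing criterion means O1-O3 if that is intended.
4. State what follows from a signal on the added contrasts. That decision is for the sponsor and those monitoring safety.

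The cost is a reworded paragraph and a few analyses of data in hand, with no extra visits, instruments or participants. Two downsides should be stated in the text. With about 16 people, even the O1-O2 contrasts would miss a 0.8 SD loss in roughly 29-60% of cases (100 − 71 to 100 − 40). The added contrasts also raise the chance of a false signal on one measure from about 4.9% to at most 12.5%.
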